6.9. Safety Analyses

All patients who receive at least 1 dose of any study therapy will be evaluated for safety and toxicity.

The MedDRA Version 22.0 (or higher) will be used when reporting AEs by MedDRA terms. The MedDRA Lower Level Term (LLT) will be used in the treatment-emergent computation. Treatment-emergent adverse events will be summarized by System Organ Class (SOC) and by decreasing frequency of Preferred Term (PT) within SOC.

Safety analyses will include summaries of the following:

- DLTs at each DL in the dose escalation phase and DLT-equivalent AEs for expansion cohorts;
- AEs, including severity and possible relationship to study drug;
- SAEs, including possible relationship to study drug;
- AEs leading to dose adjustments;
- discontinuations from study treatment due to AEs or death;
- treatment emergent abnormal changes in laboratory values;
- treatment emergent abnormal changes in vital signs and ECGs.

6.9.1. Extent of Exposure

LY3475070 will be administered PO QD on a 28-day cycle until PD, unacceptable toxicity or other criterion for study discontinuation is met. In the absence of PD, unacceptable toxicity or other criterion for study discontinuation is met, pembrolizumab may be administered for a maximum duration of 24 months (35 cycles).

Pembrolizumab will be administered IV 200mg Q3W in cohorts B, C1, D1 and E.

The actual cumulative dose taken of LY3475070 will be derived from the difference between the total number of tablets/capsules dispensed and returned over the course of the patient's treatment taking into account the dose strengths.

The duration of therapy for the QD schedule will be calculated as last dose date-first dose date+1.

A summary of exposure will be provided for each study drug, including cycle received, cumulative dose, and duration of therapy.

A summary of dose intensity will be provided for each study drug. Dose intensity (per day) is calculated as total actual dose taken/duration of therapy (day). Relative dose intensity is calculated as $100 \times (\text{actual dose intensity per day}/\text{planned dose intensity per day})$.

Note that planned dose is the same as actual dose if there is no dose modification or cycle delays.

A summary of dose adjustments will be provided for each study drug, including dose omissions, dose reductions, cycle delays, and the corresponding reasons for dose adjustment.

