### 6.1. Study Intervention(s) Administered

Cohort	Dose Level	Oral LY3475070	IV Pembrolizumab
Cohort A	DL1	150mg QD	N/A
	DL2	300mg QD	N/A
	DL3	600mg QD	N/A
	DL4	1000mg QD	N/A
Cohort B	CDL1	150mg QD	200 mg Q3W
	CDL2	300mg QD	200 mg Q3W
	CDL3	600mg QD	200mg Q3W
Cohorts C1, D1 and E	RP1D c	RP1D/MTD	200 mg Q3W
Cohorts C2 and D2	RP1D m	RP1D/MTD	N/A

Abbreviations: CDL = combination dose level; DL = dose level; IV = intravenous; N/A = not applicable; MTD = maximum tolerated dose; RP1D = recommended phase 1 dose; RP1Dc = recommended phase 1 dose (for combination therapy); RP1Dm = recommended phase 1 dose (for monotherapy); Q3W = every 3 weeks; QD = once a day.

Note: Pembrolizumab should be administered for a maximum duration of 24 months (35 cycles).

A delay of a treatment day up to 7 days due to holidays, weekends, bad weather, unrelated medical events, or other unforeseen circumstances will be permitted and not be counted as a protocol deviation. The reason for interruption should be documented on the electronic case report form (eCRF).

The doses of LY3475070 will be administered at approximately the same times on each day, generally at home. Patients should be instructed take LY3475070 on an empty stomach, if possible. Otherwise, drug capsules may be taken a minimum of 1 hour before eating or 2 hours after consumption of food. A LY3475070 administration patient diary must be kept for dosing compliance monitoring. The actual time of dose administrations will be transcribed and provided to the sponsor.

If BID dosing is evaluated, patients will take doses 12±2 hours apart (i.e., 10 to 14 hours between doses). There should at least be 10 hours between each subsequent dose.

At clinic visits, patients will be directed to take LY3475070 at the site. LY3475070 will be administered 30 to 60 minutes post administration of pembrolizumab.

Pembrolizumab will be administered using IV infusion on Day 1 of each 3-week treatment cycle after all procedures and assessments have been completed. Pembrolizumab will be administered as a dose of 200 mg using a 30-minute IV infusion. Sites should make every effort to target infusion timing to be as close to 30 minutes as possible. However, given the variability of

infusion pumps from site to site, a window between 5 minutes prior to and 10 minutes after administration is permitted (i.e., infusion time is 30 minutes (-5 min/+10 min).

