### **7.1. Discontinuation of Study Intervention**

Discontinuation of study treatment does not represent withdrawal from the study.

Participants may discontinue study treatment at any time for any reason or be discontinued from the study treatment at the discretion of the investigator should any untoward effect occur. In addition, a subject may be withdrawn by the investigator or the sponsor if enrollment into the trial is inappropriate, the trial plan is violated or for administrative and/or other safety reasons.

A subject must be discontinued from the trial for the following reasons:

- the participant or the participant's designee, for example, parents or legal guardian requests to discontinue investigational product.
- the subject is lost to follow -up

A subject must be discontinued from trial treatment but continue to be followed for any of the following reasons:

- the patient becomes pregnant during the study
- the patient is significantly noncompliant with study procedures and/or treatment
- disease progression. Disease progression should be confirmed per iRECIST 4 to 8 weeks after site-assessed first radiologic evidence of PD in clinically stable participants. Participants, who have unconfirmed disease progression may continue on treatment at the discretion of the investigator until progression per iRECIST. Any participant deemed clinically unstable should be discontinued from study treatment at first radiologic evidence of PD and is not required to have repeat tumor imaging for confirmation of PD by iRECIST.
- unacceptable toxicity
- the patient, for any reason, requires treatment with another therapeutic agent that has been demonstrated to be effective for treatment of the study indication. Discontinuation from study invention will occur prior to introduction of the new agent.
- Recurrent Grade 2 pneumonitis
- Discontinuation of treatment may be considered for participants who have attained a confirmed complete response (CR) and have been treated for at least 8 cycles (at least 24 weeks), receiving [for monotherapy: at least 2 doses of pembrolizumab; for

combination treatment: 2 cycles of the combination including 2 doses of pembrolizumab and at least 75% of the planned doses of LY3475070] beyond the date when the initial CR was declared.

- Pembrolizumab will be discontinued after completion of approximately 2 years of treatment with pembrolizumab (completion of 35 treatments with pembrolizumab).  

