For patients with non-measurable disease, PSA evaluations will be utilized for response assessment to treatment. Prostate-specific antigen will be measured at each treatment cycle (every 3 weeks), but because favorable PSA response to treatment may be delayed, early PSA rises should be ignored until 12 weeks unless patient is rapidly progressing (new lesions on image assessment) with clinical deterioration. After the first evaluation at 12 weeks, PSA response should be evaluated at every 9 weeks for progression. A PSA increase of  $\geq 25\%$  and  $\geq 2$  ng/dL from baseline/nadir, confirmed with a second measurement at least 3 weeks apart, will be considered progression. A PSA decrease from baseline that is  $\geq 50\%$  will be considered a response and should be confirmed with a repeat measurement at least 3 weeks apart.

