6.3. Patient Disposition

A detailed summary of patient disposition will be provided. It will include a summary of the number and percentage of patients entered into the study, and treated as well as number and percentage of patients completing the study (patients who receive 1 cycle of study dose or are evaluable for DLT for Phase 1a and patients who have at least 1 postbaseline tumor assessment for Phase 1b), or discontinuing (overall and by reason for discontinuation of LY3475070). Reason for discontinuation from both the study treatment and the study will be summarized by predetermined categories.

A listing of primary reasons for study treatment and study discontinuation will also be provided.

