6.12. Interim Analyses and Data Monitoring

In the Phase 1a portion of this study, dose-escalation data (monotherapy and combination) will be reviewed for safety on a cohort-by-cohort basis, until the MTDs (or the highest DLs if MTDs are not reached) are determined for each treatment part. The purpose of these cohort-by-cohort reviews is to evaluate the safety data at each DL and determine if a DLT has been observed that would suggest MTD has been met or exceeded. The investigators and the Lilly study team will make the determination regarding dose escalation based upon their review of the safety and tolerability data as described in this protocol.

In the Phase 1b portion of this study, a safety review will be performed after the first 20 patients across all dose-expansion cohorts are enrolled and treated for 1 cycle, and then every 6 months afterward. For preliminary efficacy evaluations, the following interim analyses are planned:

- Cohort C (patients with CD73+ tumors) and Cohort D (castrate resistant prostate cancer): for each cohort, an interim analysis of safety and efficacy is planned after 10 patients in

the monotherapy arm are treated and completed 2 cycles or have discontinued before the first post-baseline tumor assessment. Per 2:1 randomization ratio, at this interim analysis approximately 20 patients in the combination arm are treated. Preliminary efficacy will be evaluated on these 20 patients in the combination arm and on these 10 patients in the monotherapy arm, and the combination arm may be expanded with additional 20 patients if the totality of data support.

- Cohort E (TNBC): an interim of safety and efficacy is planned after approximately 20 patients are treated and completed 2 cycles or have discontinued before the first post-baseline tumor assessment. The trial may continue to enroll 20 additional patients for the final analysis if the totality of data supports the addition of patients.

The interim analyses may be combined if they are expected to occur within a similar timeframe; interim analyses may also be combined with any prespecified safety review or annual reporting (such as an update to the IB or Development Safety Update Review, etc.).

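### SAP 6.9.1 puts LY3475070 on a 28-day cycle while the protocol counts in 21-day cycles, so any by-cycle output for LY3475070 has two possible readings

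*SAP*

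**What the plan says.** SAP 6.9.1 (Extent of Exposure) says "LY3475070 will be administered PO QD on a 28-day cycle". The next sentence of that paragraph says that "pembrolizumab may be administered for a maximum duration of 24 months (35 cycles", and the following line says "Pembrolizumab will be administered IV 200mg Q3W in cohorts B, C1, D1 and E".

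The protocol's Schedule of Activities (Section 1.3) is headed with a 21-day cycle. Protocol 6.1 gives pembrolizumab on "Day 1 of each 3-week treatment cycle". Protocol 8.1.3 says "Prostate-specific antigen will be measured at each treatment cycle (every 3 weeks", and Protocol 7.1 refers to patients who "have been treated for at least 8 cycles (at least 24 weeks".

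The SAP uses the cycle as a unit in several places:

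- cycles received (6.5 and 6.9.1) and cycle delays (6.9.1);
- Phase 1a completion, one route to which is "patients who receive 1 cycle of study dose" (6.3);
- DLT-equivalent toxicities after Cycle 2 in Phase 1a (6.9.2);
- ECG summaries by cycle (6.9.6);
- the Phase 1b safety review after 1 cycle, and the efficacy interims, which for Cohorts C and D wait until 10 patients in "the monotherapy arm are treated and completed 2 cycles" or stopped before the first scan (6.12).

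Table JZMA.6.1 numbers days within a cycle from the first dose in that cycle. It gives no cycle length and no source for the cycle start.

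**The concern.** The SAP's only stated cycle length for LY3475070 disagrees with the protocol that schedules the visits. Version lag does not explain this. SAP Version 1 was written to protocol amendment (a), and none of the listed amendments reports a change of cycle length. Elsewhere in the SAP, 28 days is the DLT observation period (5.1.1, 5.1.3, Table JZMA.6.1). Carry-over from there is plausible but not documented.

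The choice matters because LY3475070 is dosed every day, so no single dose marks the opening of a cycle. In the monotherapy cohorts (A, C2, D2) there is no infusion to mark it either. Anchoring to the first dose of the cycle therefore works only with a cycle length or a recorded visit date. A programmer who takes the length from SAP 6.9.1 would produce counts that do not match the visits. Because exposure is summarized for each drug, one combination patient could carry two different cycle counts.

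**Working it through.** **Inputs.** 28 days (SAP 6.9.1); 21 days (Protocol 1.3 and 6.1); 24 months and 35 cycles (SAP 6.9.1); 8 cycles and 24 weeks (Protocol 7.1). One month is taken as 365.25/12 = 30.44 days.

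**Step 1: reproduce the plan's own figures.**

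- 24 months = 24 × 365.25/12 = 730.5 days. At 21 days, 730.5/21 = 34.8 cycles, which agrees with the stated 35. At 28 days, 730.5/28 = 26.1, which does not.
- 8 cycles at 21 days = 168 days = 24 weeks, as stated. At 28 days, 8 × 28 = 224 days = 32 weeks.

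The cycle-to-time conversions in the SAP section and in the protocol thus both fit 21 days. The SAP conversion concerns pembrolizumab.

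**Step 2: what changes if 28 days is used to build LY3475070 cycles** (patient without delays).

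| Item | 21 days | 28 days | Difference |
|---|---|---|---|
| Cycles in 168 days | 168/21 = 8 | 168/28 = 6 | 25% lower |
| Cycles in 252 days | 252/21 = 12 | 252/28 = 9 | 25% lower |
| 1-cycle safety review (SAP 6.12) | day 21 | day 28 | 7 days |
| 2-cycle interim trigger (SAP 6.12) | day 42 | day 56 | 14 days |
| DLT-equivalents after Cycle 2 (SAP 6.9.2) | after day 42 | after day 56 | 14 days |

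The general ratio is 1 − 21/28 = 0.25.

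**Step 3: ECG summaries.** Protocol 1.3.1 schedules a predose ECG on Cycle 2 Day 1, which is day 21 + 1 = 22. In 28-day bins, Cycle 1 runs from day 1 to day 28, so this ECG falls in Cycle 1. The Cycle 3 Day 1 ECG (day 43) falls in Cycle 2 (days 29 to 56).

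**Step 4: completion.** SAP 6.3 counts a Phase 1a patient as complete after one cycle of dosing or if DLT evaluable. With under 21 days of dosing, the one-cycle route fails under both lengths; with 28 days or more it is met under both. Only 21 to 27 days differ, and only if the patient is not DLT evaluable. Table JZMA.6.1 accepts 75% of doses with 28 days of follow-up, and 0.75 × 28 = 21 doses. A patient with 21 doses who is followed to day 28 would therefore usually be evaluable, so the affected group should be small. Phase 1b completion needs a postbaseline tumor assessment and involves no cycle.

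**Step 5: what does not change.** In SAP 6.9.1, cumulative dose comes from units dispensed and returned. Duration is last minus first dose date plus 1, and dose intensity is per day. None uses cycle length.

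**The case against.** The strongest reply is that nothing in the SAP applies the 28-day figure. Cycle Day is tied to dosing dates, cycles received has no formula, and the protocol, which governs conduct, defines the cycle. If the programmer takes cycles from recorded visits, every output is correct. This stands, and it rules out several stronger readings that a reader might infer:

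- **That the analyses are wrong as programmed from the SAP.** The 25% shortfall arises only if elapsed days are divided by 28, which the SAP does not instruct.
- **That completer status is generally affected.** It is not, beyond the Phase 1a group in step 4.
- **That the interim trigger is wrong.** The SAP and Protocol 9.5 word it in effect identically, so there is at most a 14-day ambiguity. Patients who stop before the first scan count either way, Protocol 6.1 allows treatment-day delays of up to 7 days, and Protocol 9.1 plans no formal test of response rate. No error rate is at stake.
- **That the pembrolizumab limit stretches to 32.2 months** (35 × 28 = 980 days; 980/30.44 = 32.2). The SAP keeps pembrolizumab on every 3 weeks, so no document produces this figure.

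The reply does not make the line harmless. The SAP names no visit or form field as the source of cycle starts, so a literal reader has only the 28-day statement to use for a daily drug.

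**Conclusion.** The contradiction is real and should be corrected. It is a defect in an analysis counting unit, and its consequences are conditional on 28 days being used to build cycles. On that condition, LY3475070 cycles received are 25% too low against the protocol schedule, ECG visits are assigned to the wrong cycle, and the DLT-equivalent summary starts 14 days later. The safety review and interim timings are open by 7 and 14 days. The figures assume a patient without delays.

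Two neighboring matters are separate. The SAP starts the DLT-equivalent summary after Cycle 2, although the DLT observation period ends at day 28. That leaves days 29 to 42 or days 29 to 56 outside both summaries, so the gap exists under either cycle length. Also, the first scan is due at 9 weeks ± 7 days (day 56 to 70), so a day-42 trigger would precede any scheduled scan. Settling the cycle length resolves neither.

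**What to change.** Reconcile the cycle statement in SAP 6.9.1 with the protocol's Schedule of Activities. Add to Table JZMA.6.1 a single definition of a cycle, giving its source (for example, the recorded Day 1 visit) and its length, to be used for counting in both drugs. Keep the 28-day DLT observation period as a separately named quantity. Then check that SAP 6.3, 6.5, 6.9.1, 6.9.2, 6.9.6 and 6.12 all use that definition.

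The cost is one corrected line and one added table row in the SAP. No data collection changes. Because LY3475070 is taken daily, this settles how cycles are counted and alters no dose or administration rule.

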6.9.2. Adverse Events

Adverse event (AE) verbatim terms will be provided by the investigators and then will be mapped by Lilly or its designee to corresponding terminology within the Medical Dictionary for Regulatory Activities (MedDRA) Lower Level Term (LLT) dictionary Version 22.0 (or higher).

The investigator will use Common Terminology Criteria for Adverse Events (CTCAE) Version 5.0 (NCI 2009) to assign AE severity grades.

Preexisting conditions are defined as AEs that begin but do not resolve prior to the first dose of study drug in each study period. Preexisting conditions will be presented by patient and can be combined with the listing of AE, so that the history of the preexisting conditions/AEs can be traced.

A treatment emergent adverse event (TEAE) is defined as any AE that begins on or after the day of first dose in the reporting study period or any preexisting condition that increases in CTCAE grade on or after the day of first dose in the reporting study period. The MedDRA LLT will be used in the treatment-emergent computation.

The number of patients who experienced a TEAE, or TEAE possibly related to study drug, will be summarized. Treatment-emergent adverse events will be summarized by System Organ Class (SOC), by Preferred Term (PT) of decreasing frequency within SOC, and by maximum CTCAE grade and grade categories (any, Grade 3 or higher).

Adverse events leading to dose adjustments, treatment discontinuation, or death will also be summarized.

Dose-limiting toxicities in Phase 1a and DLT-equivalent toxicities occurring after Cycle 2 in Phase 1a or any cycle in Phase 1b will be summarized by cohort.

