### Intervention Groups and Duration

Cohort	Dose Level	Oral LY3475070	IV Pembrolizumab
Cohort A	DL1	150mg QD	N/A
	DL2	300mg QD	N/A
	DL3	600mg QD	N/A
	DL4	1000mg QD	N/A
Cohort B	CDL1	150mg QD	200 mg Q3W
	CDL2	300mg QD	200 mg Q3W
	CDL3	600mg QD	200mg Q3W
Cohorts C1, D1 and E	RP1D c	RP1D/MTD	200 mg Q3W
Cohorts C2 and D2	RP1D m	RP1D/MTD	N/A

Abbreviations: CDL = combination dose level; DL = dose level; IV = intravenous; MTD = maximum tolerated dose; N/A = not applicable; Q3W = every 3 weeks; QD = once a day; RP1D = recommended phase 1 dose; RP1Dc = recommended phase 1 dose (for combination therapy); RP1Dm = recommended phase 2 dose (for monotherapy).

[figure not shown]
[figure not shown]
Note: Pembrolizumab should be administered for a maximum duration of 24 months (35 cycles).

LY3475070 is to be administered until PD, unacceptable toxicity or other criterion for study discontinuation is met. In the absence of PD, unacceptable toxicity or other criterion for study discontinuation is met; pembrolizumab may be administered for a maximum duration of 24 months (35 cycles).

The above table shows the provisional dose levels that will be explored, ranging from 150 mg to 1000 mg QD of LY 3475070. Depending on PK, pharmacodynamic, and safety data observed, not all the provisional dose levels may be explored. A dose level -1 (DL-1 = 75 mg) may be explored if a dose of 150 mg QD (DL1) is not tolerated or if otherwise warranted based on the assessment of PK, PD, and safety data. Intermediate and/or higher dose levels as well as alternative schedules (e.g., 2 times a day [BID] dosing instead of QD) may be explored after discussion between Lilly and investigators if deemed appropriate based on the assessment of patient safety, PK, and PD data. The total dose of LY3475070 is not planned to exceed 1200 mg per 24 hours. If BID dosing is evaluated, patients will take doses 12±2 hours apart (i.e., 10 to 14 hours between doses). There should at least be 10 hours between each subsequent dose.

**Data Monitoring Committee:** No

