### 6.1.1. Definition of DLT and DLT-ET

#### 6.1.1.1. DLT

A DLT is defined as any of the events listed in the table below, if both of the following criteria are met:

- the event occurs during the DLT observation period (28 days) in Phase 1a, and
- the event cannot, in the opinion of the investigator, be definitely attributed to primary disease or extraneous causes, such as accident.

Patients who experience a DLT in the DLT observation period will be discontinued from study treatment.

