**6.1.1.2. DLT-ET**

A **DLT-equivalent toxicity (ET)** is any event listed in Section 6.1.1.1 occurring after the DLT observation period in Phase 1a or any cycle in Phase 1b.

A DLT-ET is an AE that meets the DLT criteria as defined above and occurs in any cycle other than the DLT assessment period (28 days for Cohorts A1 through A4 and B1 through B3). In addition to the DLT assessment period, available safety data beyond the DLT assessment period may also be taken into consideration prior to a decision to advance to the next DL or the determination of the RP2D.

Potential DLTs that are AEs, which are reasonably anticipated AEs for concomitant medication should be reviewed by the treating investigator and Lilly CRP/CRS before final determination as a DLT. Review and discussion may include additional participating investigators. Such review

may determine that confounding factors render the case to be not evaluable for the purposes of dose selection.

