5.1.1. Phase 1a Dose Escalation

Phase 1a of the study will target the following tumor types: triple negative breast cancer, pancreatic cancer, PD-1 refractory NSCLC, PD-1 refractory RCC, PD-1 refractory melanoma, metastatic castrate resistant prostate cancer (mCRPC) and ovarian cancer. In **Cohort A** in Phase 1a, escalating doses of single agent LY3475070 will be evaluated in at least 3 evaluable patients per dose level (i.e., DLA1-A4). The dose limiting toxicity (DLT) observation period will be 28 days. The first patient of each DL will be observed for 48 hours before additional patients are enrolled to that DL. The totality of safety data will be reviewed by the Lilly clinical research physician/clinical research scientist (CRP/CRS) and study investigators prior to escalating to a next DL. Intra-patient dose escalation is not allowed.

It is anticipated that a minimum of 4 DLs will be evaluated in Cohort A to determine the MTD of single agent LY3475070, or, in the absence of MTD, a recommended Phase 1b dose of single agent LY3475070. The final MTD will be the dose for which the estimated toxicity rate is the closest to the target toxicity rate of 30% and less than 35%. The recommended Phase 2 dose (RP2D) to be formally established in Phase 1b part of the study will be based upon the totality of safety, PK and pharmacodynamic data, and thus may be lower than the MTD or the recommended Phase 1b dose identified in the Phase 1a part of the study.

Once the DLA2 (300 mg QD) for single agent LY3475070 is determined safe and enrollment to DL3 has commenced, LY3475070 in combination with pembrolizumab will be evaluated in **Cohort B** in 3 to 6 patients starting at combination DL1 (150 mg QD LY3475070 and pembrolizumab) and escalated, independently from ongoing monotherapy dose escalation, to the recommended Phase 1b dose or MTD of LY3475070 single agent. The first patient of each DL will be observed for 48 hours before additional patients are enrolled to that DL. There will be no dose escalations for pembrolizumab, which will be given at 200 mg every 3 weeks (Q3W). The dose given in the dose escalation in Cohort B should not exceed the maximum dose shown to be safe in Cohort A.

Figure JZMA.5.1 illustrates the study design for Phase 1a dose escalation. Section 5.1.3 describes the details of the dose-escalation method used in this study.

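### SAP 6.9.2 starts the Phase 1a DLT-equivalent summary after Cycle 2, so DLT-criteria events on nominal Days 29 to 42 fall in neither the DLT nor the DLT-equivalent summary

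*SAP*

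**What the plan says.** Protocol 6.1.1.1 requires for a DLT that "the event occurs during the DLT observation period (28 days) in Phase 1a". SAP 5.1.1 uses the same window: "The dose limiting toxicity (DLT) observation period will be 28 days".

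Protocol 6.1.1.2 says that a DLT-equivalent toxicity "is any event listed in Section 6.1.1.1 occurring after the DLT observation period in Phase 1a or any cycle in Phase 1b". For Phase 1a that means from Day 29. Protocol 4.1.1 adds a second kind: an event in a backfill patient that meets the DLT criteria inside the DLT period is also DLT-equivalent.

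SAP 6.9.2 uses a different start: "DLT-equivalent toxicities occurring after Cycle 2 in Phase 1a or any cycle in Phase 1b will be summarized by cohort".

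The cycle length differs between the documents. The Schedule of Activities (Protocol 1.3) sets a cycle at 21 days. SAP 6.9.1 says "LY3475070 will be administered PO QD on a 28-day cycle until PD".

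The bullet lists of safety summaries in SAP 6.9 and Protocol 9.4.4 name DLT-equivalents for the expansion cohorts only. The sentence in SAP 6.9.2 is therefore the only planned summary of DLT-equivalents in Phase 1a.

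**The concern.** In patients enrolled for escalation, the DLT and DLT-equivalent summaries should meet without a gap: one takes DLT-criteria events inside the observation window, the other takes them afterwards. The protocol's definitions do this. The SAP ends the first summary on a day count and starts the second at the end of a cycle, and the two points do not coincide.

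DLTs and safety are the Phase 1a primary endpoints. Protocol 6.1.1.2 allows safety data from beyond the window to inform the next dose level and the RP2D. Protocol 4.1 says that DLT-equivalents in backfill patients feed into escalation and RP2D selection, and the monitoring rule in Protocol 9.2 counts DLTs and DLT-equivalents together. At stake is whether the reported DLT-equivalent count is complete and agrees with the protocol's own definition.

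**Working it through.** Inputs:

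- DLT window: Days 1 to 28 (Protocol 6.1.1.1; SAP 5.1.1). Protocol 9.3 uses 3 weeks in defining the DLT-evaluable population, but that governs which patients count, not when an event qualifies.
- Protocol start of DLT-equivalents in Phase 1a: Day 29 (Protocol 6.1.1.2).
- SAP start: the day after Cycle 2 ends (SAP 6.9.2).
- Cycle length: 21 days (Protocol 1.3) or 28 days (SAP 6.9.1).
- Permitted delay of a treatment day: up to 7 days (Protocol 6.1).

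**Step 1. Check the cycle length against the plan's own figure.** The synopsis equates 35 pembrolizumab cycles with 24 months. With one month = 365.25 / 12 = 30.4375 days:

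- 21-day cycle: 35 × 21 = 735 days; 735 / 30.4375 = 24.15 months, which reproduces the figure.
- 28-day cycle: 35 × 28 = 980 days; 980 / 30.4375 = 32.2 months, which does not.

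The 35-cycle figure concerns pembrolizumab and the 28-day statement concerns LY3475070, but the Schedule of Activities uses one cycle for both drugs. The main calculation therefore uses 21 days, and 28 days is shown as a sensitivity case.

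**Step 2. Find the uncovered interval.** Last day of Cycle 2 = 2 × cycle length + any delay. Uncovered days = last day of Cycle 2 − 28.

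| Reading of Cycle 2 | Last day | SAP summary starts | In neither summary |
|---|---|---|---|
| 21-day cycle | 42 | Day 43 | 42 − 28 = 14 days (29 to 42) |
| 21-day cycle, one 7-day delay | 49 | Day 50 | 49 − 28 = 21 days (29 to 49) |
| 28-day cycle | 56 | Day 57 | 56 − 28 = 28 days (29 to 56) |

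Neither cycle length removes the gap, and the protocol's nominal cycle gives the smallest one.

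**Step 3. Try a looser reading.** Suppose the SAP meant from the start of Cycle 2. On a 21-day cycle that is Day 22, which overlaps the DLT window on Days 22 to 28. On a 28-day cycle it is Day 29, which would match the protocol, but only by departing from both the SAP's wording and the protocol's cycle length.

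**Step 4. Check backfill patients.** Protocol 4.1.1 makes their in-window DLT-criteria events DLT-equivalent. A summary that starts after Cycle 2 excludes these too, and so would one that starts on Day 29. Up to 20 patients are concerned. The SAP is based on protocol amendment (a), and amendment (d) added the backfill language, so the SAP could not have allowed for it.

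**The case against.** The strongest reply is that this is one phrase in one descriptive summary. Much of that stands.

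- **No data are lost.** A Day 29 to 42 event still appears in the TEAE tables by maximum grade, in the Grade 3 or higher category if it qualifies, and where applicable among SAEs and AEs leading to dose adjustment, discontinuation or death.
- **No decision rule changes.** DLTs are events of Days 1 to 28, so the DLT endpoint and the mTPI-2 decisions are unaffected. The stopping boundaries are set out in Protocol 9.2 and do not use the SAP's wording. Escalation rests on joint review of all safety data (Protocol 4.1), and the RP2D on all the evidence together (Protocol 6.1.2).

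A reader might therefore infer too much in four ways:

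- That toxicity is understated at every dose level in the table that supports the recommended dose. No section ties dose selection to this table, and a level is affected only if a qualifying event falls in the gap.
- That a fixed share of DLT-equivalent follow-up is missing. Stopping the count at the 9-week scan (Day 63) gives 14 / (63 − 28) = 14 / 35 = 40%, or 28 / 35 = 80% on a 28-day cycle. But treatment continues until progression and AEs are collected through the 90-day visit. Treatment to Day 126 gives 14 / (126 − 28) = 14 / 98 = 14%. Stopping on Day 63 with follow-up to about Day 153 gives 14 / (153 − 28) = 14 / 125 = 11%. The documents set no denominator.
- That every Phase 1a patient loses 14 days. This applies only to patients still followed after Day 28.
- That the gap directly follows the second pembrolizumab dose. That dose falls nominally on Day 22, so the next week lies inside the DLT window. Cohort A receives no pembrolizumab.

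The reply does not remove the inconsistency. The general tables do not apply the DLT criteria. Grade 3 or higher includes events those criteria exclude, such as Grade 3 or 4 lymphopenia, and leaves out some they include, such as an immune-related event of lower grade that forces permanent discontinuation. A reader of the report could not rebuild the missing count from them.

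**Conclusion.** The SAP is wrong as written on this point. Followed literally, it leaves a nominal 14-day interval, Days 29 to 42, in which a Phase 1a event meeting the DLT criteria is reported neither as a DLT nor as a DLT-equivalent. The DLT-equivalent count can be understated wherever such an event occurs. How many events that means cannot be estimated from the documents.

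The 14 days rest on the protocol's 21-day cycle with no delays. A permitted 7-day delay makes it 21 days, and the cycle length printed in SAP 6.9.1 makes it 28. The existence of the gap does not depend on that choice.

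The importance is moderate: an incomplete safety summary in a first-in-human study, to be corrected before analysis. It does not show that escalation, stopping or dose selection would be distorted.

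**What to change.** In SAP 6.9.2, replace the Phase 1a part of the sentence so that the summary covers *DLT-criteria events after the 28-day DLT observation period in Phase 1a, plus DLT-criteria events within that period in backfill patients (Protocol 4.1.1)*. The Phase 1b part can stay. Anchoring to a day count also makes the summary independent of cycle length and treatment delays.

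The backfill clause is needed. Moving the start to Day 29 alone would still omit events that Protocol 4.1.1 classes as DLT-equivalent. Protocol 6.1.1.2 defines DLT-equivalents only outside the window, so it should be reconciled with 4.1.1 in the same pass.

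Two further alignments belong with this change:

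- Extend the bullet in SAP 6.9 to DLT-equivalents in Phase 1a, since it now names the expansion cohorts only.
- Reconcile the 28-day cycle in SAP 6.9.1 with the 21-day cycle in Protocol 1.3.

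The cost is a few lines of SAP text, a date cut-off and a backfill flag in the programming. No new data are collected.
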